11.5 AE Follow-up

AEs should be followed to resolution or stabilization, and reported as SAEs if they become serious. This also applies to subjects experiencing AEs that cause interruption or discontinuation of investigational product, or those experiencing AEs that are present at the end of their participation in the study; such subjects should receive post-treatment follow-up as appropriate. If an ongoing AE changes in its severity or in its perceived relationship to study drug, a new AE entry for the event should be completed.

11.6 Reporting of AE Information Following Study Completion

Collection of safety information following the end of investigational product administration is important in assisting in the identification of possible delayed toxicities or withdrawal effects. All SAEs must be collected which occur within 56 days of discontinuation of dosing or completion of the subject's participation in the study if the last scheduled visit occurs at a later time. In addition, the Investigator should report any SAE which may occur after this time period which they believe to be certainly, probably or possibly related to investigational product. Finally, all events of death, graft loss, malignancy, PTLD, and serious infections (i.e., otherwise meeting SAE reporting requirements) must be reported for all randomized subjects until the end of the study, irrespective of study drug discontinuation or investigator-deemed causality.

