Protocol Title: Use of Belatacept during Post Depletional Repopulation to Facilitate Tolerance in Renal Allograft Recipients

Investigator: [name]

Protocol Date: 10Jul2015

NCT Number: NCT00565773

SYNOPSIS

| |
|-----------------------------------------------------------------------------------------------------------------------------------------------------------------------------------------------------------------------------------------------------------------------------------------------------------------------------------------------------------------------------------------------------------------------------------------------------------------------------|
| Title of Study: Use of Belatacept During Post Depletional Repopulation to Facilitate Tolerance in Renal Allograft Recipients |
| Study Phase: II |
| IND Sponsor: [name] PhD |
| Participating Site: Emory University |
| Study Design: Single-center, open-label, proof-of-concept study in non-HLA-identical live and deceased donor renal transplants. |
| Duration of Study: Subjects will be enrolled over a one-year period and followed for up to five years. |
| Number of Subjects: Approximately 40 |
| Study Population: Adult, EBV seropositive patients who do not have evidence of DSA pretransplant and who are scheduled to receive a kidney transplant at Emory University. Candidacy for transplantation will be determined using the standard methods of evaluation active at Emory during the study period. |
| Primary Objective: To determine whether lymphocyte depletion with alemtuzumab followed by belatacept and sirolimus will permit renal allograft function without rejection, and will allow for a general population of renal transplant recipients to be weaned to belatacept monotherapy for maintenance immunosuppression. The primary endpoint will be the number of patients successfully withdrawn from sirolimus for 1 year after their last dose of sirolimus. |

Secondary Objectives:

- 1) Determination of the prognostic ability of assays based on surface phenotype changes seen during homeostatic repopulation, including Ki67 expression, T_{REG} and B_{TRANS} cell surface phenotypes, and T_M to T_{REG}/B_{TRANS} balance, with regard to the anticipation of successful immunosuppressive drug withdrawal.
- 2) Assessment of the proposed therapies to prevent biopsy proven acute rejection at 1, 3 and 5 years post-transplant compared to the standard reported in the SRTR database for similar patients.

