3 STUDY DESIGN AND EVALUATION

3.1 Study Design

This will be a single-center, open-label, non-randomized, proof-of-concept study in recipients of living or deceased donor renal transplants (DDRTs). Twenty renal transplant patients will be enrolled, at least 10 of which will be recipients of DDRTs. At the time of transplantation, participants will be given alemtuzumab, 30mg intravenously over three hours. Participants will receive combination maintenance therapy with sirolimus and belatacept for at least one year. Patients' absolute lymphocyte counts (ALCs) and percent expression T cell of Ki67 will be assessed monthly. After one year of therapy, participants may consent to and begin sirolimus withdrawal or continue therapy through study close. Patients wishing to withdraw from sirolimus will begin sirolimus weaning when their ALC has reached at least 80% of baseline and had two consecutive monthly assessments of their percent expression of Ki67 fall within at least one standard deviation of the Ki67 expression of a healthy control population. Weaning will be triggered of the Ki67 expression, with other surface phenotype assessments being followed observationally. Patients meeting these parameters will be weaned off of sirolimus by halving the dose and/or increasing the dosing interval over at least a three-month period. Each dose reduction will require stable (within 1 standard deviation) peripheral Ki67 expression. After sirolimus is discontinued, patients will remain on belatacept monotherapy indefinitely. Clinical and mechanistic observation will continue for the duration of the study to assess the efficacy and safety of this approach. Subjects will be followed for at least five years.

Duration of Study

Subjects will be followed for at least five years. Belatacept is now approved by the FDA. Therefore, subjects remaining on belatacept at the conclusion of their five-year participation would be eligible to continue this therapy. If at the conclusion of this study belatacept is not commercially available to patients, the Principal Investigator will discuss other treatment options utilizing approved immunosuppressive therapies with the subject. If subjects are successfully weaned from sirolimus as a result of their participation in this protocol, there will be no need for consideration of alternative therapy.

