4 STATISTICAL METHODOLOGY

4.1 Data Set Descriptions

A summary of all patient data will be kept in a study database developed for this study. In addition to the experimental data, this database will include recipient and donor demographics and transplant relevant medical history (comorbidities, HLA type, etc.), graft function, immunosuppressive medications and levels, and a running summary of the patient's post transplant course. Data will be recorded and reported in accordance with the standards required by the United Network for Organ Sharing (UNOS). The data set will consist of all patients who are randomized and transplanted and will be used for all

efficacy analyses. The as-treated data set will consist of all patients who receive at least one dose of belatacept and will be used for all safety analyses. Subgroup analyses will be performed for selected endpoints in subjects whom withdrawal was attempted and not attempted in order to provide supporting information to the main analyses. Demographic and baseline characteristics of patients will be summarized descriptively by treatment group, by means and standard deviations (SDs) for continuous variables and frequency distribution for categorical variables. Summaries will be performed based on the data set.

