6.8 Withdrawal of Subjects from Study

Subjects will be removed from the study for the following reasons:

1. Withdrawal of informed consent (subject's decision to withdraw for any reason)
2. Any clinical adverse event, laboratory abnormality or intercurrent illness which, in the opinion of the Investigator, indicates that continued treatment with study therapy is not in the best interest of the subject
3. Pregnancy
4. Missing 2 consecutive belatacept infusions, unless the subject is receiving lymphocyte-depleting therapy or has approval by the medical monitor to remain in the study
5. Subjects requiring dialysis for 56 consecutive days and the investigator has determined that the subject no longer requires immunosuppression as the graft is functionally lost
6. Imprisonment or the compulsory detention for treatment of either a psychiatric or physical (e.g., infectious disease) illness.

Subjects who are discontinued from study therapy will be followed for safety for 8 weeks post-discontinuation.

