| BK viremia/viruria PCR | | X | | | X |
| Adverse Events | X | X | | | X |
| QoL | | | | X | |
| Neurologic Exam | | | X | | |
| Immunogenicity | | | | X ^a | |

^a These are specific study related assays for reporting purposes.

Long-Term Follow-Up Cohort 1

| Tests / Evaluations | Every 6months | Yearly |
|----------------------------------------------------------------------|----------------------|----------------|
| Telephone Reporting | X | |
| Serum Chemistry/ lipids /CBC | X | |
| Sirolimus trough | | X |
| Lymphocyte subsets | X | |
| Peripheral transcription | | X |
| CMV and EBV PCR | X | |
| BK viremia/viruria PCR | X | |
| PRA | | X |
| Anti-Donor Antibody | | X |
| Donor-specific and third party mixed lymphocyte responsiveness/ ICCS | | X |
| Renal Biopsy | | X ^b |
| Intragraft mRNA Analysis | | X ^b |
| Adverse Events | X | X |
| QoL | X | |
| Neurologic Exam | X | |
| PK | | |
| Immunogenicity | X | |

=

^b To be performed prior to weaning patient to monotherapy (generally at 12 months) and again after stable on monotherapy as clinically indicated.

Long-Term Follow-Up Cohort 2

| Tests / Evaluations | Monthly after Year 1 | Every 3 months from 6 - 24Months | Every 6 months | Yearly |
|----------------------------------------------------------------------|-----------------------------|-----------------------------------------|-----------------------|----------------|
| Telephone Reporting | | | X | |
| Serum Chemistry/ lipids /CBC | X ^c | | X | |
| Sirolimus trough ^d | X | | | X |
| Lymphocyte subsets Ki67 | | | X | |
| Peripheral transcription | | | | X |
| CMV and EBV PCR | | X | X | |
| BK viremia/viruria PCR | | X | X | |
| PRA | | | | X |
| Anti-Donor Antibody | | | | X |
| Donor-specific and third party mixed lymphocyte responsiveness/ ICCS | | | | X |
| Renal Biopsy | | | | X ^b |
| Intra-graft mRNA Analysis | | | | X ^b |
| Adverse Events | X ^e | | | |
| QoL | | | X | |
| Neurologic Exam | | | X | |
| Immunogenicity | | | X | |

^cStudy participants may have these labs drawn more or less frequently as deemed clinical necessary by the investigator.

^dStudy participants who are not weaning sirolimus and are on a stable, low dose can have trough levels monitored as frequently as a monthly basis or as clinically indicated.

^eIf study participant is on a stable dose of sirolimus, not weaning, and receiving commercial belatacept as an outpatient, then adverse events may be assessed every three months.

Year 1 Medication Flowchart

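### Section 11.6 guarantees late-event reporting only for 'randomized' subjects, which read literally leaves out the non-randomized second cohort once a subject stops therapy and is removed

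*Combined protocol and SAP*

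**What the plan says.** **Who is in the study.** The synopsis gives "Number of Subjects: Approximately 40". Section 1.2 keeps the first 20 patients under follow-up and adds a second cohort with broader entry. Section 1.3.5 reports that those first 20, all live-donor recipients, were randomized to donor marrow or none. Of the current enrolment of 20, at least 10 of them deceased-donor recipients, Section 3.1 says: "This will be a single-center, open-label, non-randomized, proof-of-concept study in recipients of living or deceased donor renal transplants".

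**Late-event reporting.** Section 11.6 has three layers:
- All SAEs are collected to 56 days after dosing stops, or to completion of participation if the last scheduled visit is later.
- After that, only SAEs that the investigator thinks certainly, probably or possibly related are reported.
- Death, graft loss, malignancy, PTLD and serious infection "must be reported for all randomized subjects until the end of the study, irrespective of study drug discontinuation or investigator-deemed causality".

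**What happens on stopping.** Sections 6.4 (stopping belatacept) and 6.8 (removal from the study) list essentially the same six reasons. Section 6.8 then says: "Subjects who are discontinued from study therapy will be followed for safety for 8 weeks post-discontinuation". Section 6.4 says the same.

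**Safety analysis.** Section 4.1: "The as-treated data set will consist of all patients who receive at least one dose of belatacept and will be used for all safety analyses". Section 4.2 tabulates AEs and SAEs by treatment group, a term the plan does not define for this design.

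**AE schedule.** In Section 8.1 the long-term table for cohort 1 has the row "Adverse Events | X | X" under the six-monthly and yearly columns. The cohort 2 table puts AEs under "Monthly after Year 1". Its footnote e allows three-monthly assessment for a subject on stable sirolimus, not weaning, and receiving commercial belatacept as an outpatient.

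**The concern.** The third layer of Section 11.6 is the only one that secures the serious late outcomes whatever the drug status or attributed cause. Its population is defined by a word that does not describe the cohort now being enrolled. If site staff follow the text, an unrelated death, graft loss or serious infection in a removed cohort 2 subject need not be reported after week 8.

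Three parts of the plan depend on those events:
- Objective 4 compares malignancy and opportunistic infection by 1, 3 and 5 years with SRTR.
- Objective 7 compares graft function and survival with historical controls.
- The stopping rule in Section 6.9 counts severe infection, malignancy and death, among other failures, in five patients at any time.

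Missing events on the trial side alone would make the regimen look better in the two comparisons and would delay or prevent the stopping count being reached.

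A smaller, separate matter is that the two cohorts share one safety set but are asked about AEs at different intervals in long-term follow-up. A pooled or side-by-side table of non-serious AEs would partly reflect how often people were asked.

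**Working it through.** The plan gives no figure on this point to reproduce. The check is a reading of the clauses plus simple counting.

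**1. Does another clause rescue a removed cohort 2 subject?**
- *Completion-of-participation limb of 11.6.* It covers anyone still attending visits. A subject removed under 6.8 has no later scheduled visit, so cover ends at 56 days, which is the 8 weeks of 6.4 and 6.8 (8 × 7 = 56).
- *Related SAEs after the window.* These stay reportable for everyone, but only if judged at least possibly related.
- *Cancer note in 11.7.* All cases of cancer are to be reported immediately, with no cohort limit and no stated end date. This arguably covers malignancy and malignant PTLD after removal.
- *What is left.* Deaths, graft losses and serious infections judged unrelated, after day 56, in removed cohort 2 subjects.

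**2. How much time is that for one subject?** Take five years (60 months) as the end of follow-up and 56 days = 56/30.44 = 1.84 months. The uncovered share after stopping at month t is (60 − t − 1.84)/(60 − t).
- t = 12: 46.16/48 = 96.2%
- t = 36: 22.16/24 = 92.3%

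**3. How much for the cohort?** This needs a stopping rate, which the plan does not give. By assumption only: each one of 20 subjects removed at month 12 leaves 46.16/(20 × 60) = 3.8% of planned cohort person-time uncovered. If 20% stopped at month 12, the figure would be 0.20 × 46.16/60 = 15.4%. If the stops were spread evenly over five years, it would be 0.20 × [58.16²/(2 × 60)]/60 = 9.4%. The 20% is borrowed from the 17.6% and 21.1% who discontinued for AEs on belatacept in Appendix C, under a different regimen. Section 1.3.5 reports that all of the first 20 patients tolerated belatacept, so the true figure could be far lower.

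**4. AE schedule.** Scheduled assessments over the 48 months from year 1 to year 5, with cohort 1's yearly visits coinciding with six-monthly ones:
- Cohort 1: 48/6 = 8
- Cohort 2, monthly: 48/1 = 48, a ratio of 6:1
- Cohort 2, footnote e throughout: 48/3 = 16, a ratio of 2:1

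As an illustration only, suppose a non-serious AE persists or is recalled for an exponentially distributed time with mean m months, and is captured only at visits L months apart. The capture share is (m/L)(1 − e^(−L/m)).
- m = 1: 0.17 six-monthly, 0.32 three-monthly, 0.63 monthly
- m = 12: 0.79, 0.88 and 0.96 respectively

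With equal true rates, cohort 1 would then show 0.26 to 0.82 of the monthly-assessed rate, or 0.52 to 0.89 of the three-monthly rate. The documents give no value of m, and spontaneous reports (Section 11.3) would narrow the gap.

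**The case against.** The strongest reply is that 'randomized' is residual wording and not a rule. Section 4.1 uses the same word to define the efficacy set, where a literal reading would drop all of cohort 2 from the primary analysis. Section 9.3 also refers to randomization before study treatment. Section 11.6 names no cohort. This stands as an account of how the word got there, and it rules out reading the clause as a deliberate restriction. It does not make the clause reach cohort 2 as written.

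Second, a reader might infer that late deaths and malignancies in cohort 2 are simply not collected. The documents do not support that. SAEs are collected from consent for everyone (Section 11.3) and through participation (Section 11.6), and cancers carry their own reporting rule. The gap concerns removed subjects only.

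Third, a reader might infer that harm rates cannot be compared between the cohorts at all. That is too broad. The schedule difference bears on non-serious AEs; SAEs, deaths and cancers are to be reported as they occur. No cohort-against-cohort harm comparison is planned, and safety is descriptive. Section 11.3 also leaves many common non-serious events unrecorded in both cohorts unless drug-related or serious. By the time of writing, Section 1.3.5 counted 19 first-cohort patients at month 12 and 11 at month 24, so part of that cohort's follow-up ran under a version not shown here. All of this stands and limits the schedule point to a matter of presentation.

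**Conclusion.** The defect in Section 11.6 is real and should be corrected. Followed literally, the clause fails to require reporting of unrelated deaths, graft losses and serious infections more than 56 days after a cohort 2 subject stops therapy and is removed. For such a subject the uncovered share of the remaining time to year 5 is above 90% for a stop at month 12 or month 36. For the cohort as a whole the size cannot be stated, because it depends on how many subjects are removed; the percentages in step 3 are illustrations.

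Any bias would favour the regimen in objectives 4 and 7. This assumes that the registry and historical comparators count events regardless of treatment status, which the documents do not say. The Section 6.9 counts would be incomplete in the same direction. The primary endpoint is not affected by this clause.

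The AE schedule contrast, between 6:1 and 2:1, is a secondary point confined to post-year-1 non-serious AEs. It does not support a general statement that harms in the two cohorts are not comparable.

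**What to change.** (a) In Section 11.6, replace the reference to randomized subjects with 'all enrolled subjects in both cohorts'. Reconcile this with the removal and 8-week follow-up wording in Sections 6.4 and 6.8, so that it is clear that reporting of the five event types continues to the end of the study after removal, as far as consent allows when a subject has withdrawn it. The reasons for stopping therapy need not change. The same reconciliation is needed for cohort 1, for whom reporting to study end also sits beside removal at 8 weeks.

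(b) In Section 4.2, state that treatment group means cohort. Present post-year-1 non-serious AEs by cohort, with the number of AE assessments made, and do not pool them. The assessment count also shows how far footnote e was used, since frequency within cohort 2 can depend on whether a subject is weaning.

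The cost is a short wording change, continued reporting of five event types for the few subjects who stop drug, and one extra table split. No visits or procedures are added for subjects still participating.

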11.7 Handling of Serious Adverse Events (SAEs)

A *serious AE or reaction* is any untoward medical occurrence that at any dose:

- results in death,
- is life-threatening (defined as an event in which the patient or subject was at risk of death at the time of the event; it does not refer to an event which hypothetically might have caused death if it were more severe),
- requires inpatient hospitalization or prolongation of existing hospitalization, (refer to note for exceptions),
- results in persistent or significant disability/incapacity,
- is a congenital anomaly/birth defect,
- is an important medical event (defined as a medical event(s) that may not be immediately life-threatening or result in death or hospitalization but, based upon appropriate medical and scientific judgment, may jeopardize the patient/subject or may require intervention (e.g., medical, surgical) to prevent one of the other serious outcomes listed in the definition above.)

NOTE:

- Pregnancy: Incidence of pregnancy is not considered a SAE; pregnancy must, however, be reported immediately using the BMS Pregnancy Surveillance Form
- Cancer/Overdose: All cases of cancer and overdose must be reported immediately using the SAE Report Form.
- Hospitalizations (exceptions): Criteria for hospitalizations not reported as SAEs include admissions for:
 - Planned as per protocol medical/surgical procedure
 - Routine health assessment requiring admission for baseline/trending of health status documentation (e.g., routine colonoscopy)
 - Medical/surgical admission for purpose other than remedying ill health state (planned prior to entry into study trial; appropriate documentation required)
 - Admission encountered for other life circumstance that carries no bearing on health status and requires no medical/surgical intervention (e.g. lack of

housing, economic inadequacy, care-giver respite, family circumstances, administrative)

An SAE report should be completed for any event where doubt exists regarding its status of seriousness.

Adverse events classified as “serious” require expeditious handling and reporting to BMS to comply with regulatory requirements.

All serious AEs whether related or unrelated to investigational product, must be immediately reported to BMS (or designee) by confirmed facsimile transmission. If only limited information is initially available, follow-up reports are required. The original SAE form must be kept on file at the study site.

For studies conducted under an Investigator IND, any event that is both serious and unexpected must be reported to the FDA as soon as possible and, in no event, later than 7 days (death or life-threatening event) or 15 days (all other SAEs) after the investigator’s or institution’s initial receipt of the information. Bristol-Myers Squibb will be provided with a simultaneous copy via facsimile of all adverse events filed with the FDA. SAEs should be reported on the MedWatch Form 3500A, which can be accessed at:

<http://www.accessdata.fda.gov/scripts/MedWatch/>

MedWatch forms should be sent to the FDA online at the above internet address or at:

MEDWATCH
[name]
[name]
Fax: [name] ([name])

Cases of pregnancy must be reported on paper Pregnancy Surveillance Forms in lieu of SAE pages.

Collection of complete information concerning SAEs is extremely important. Thus, follow-up information which becomes available as the SAE evolves, as well as supporting documentation (e.g., hospital discharge summaries and autopsy reports), should be collected subsequently, if not available at the time of the initial report, and immediately sent using the same procedure as the initial SAE report.

In accordance with local regulations, Investigators will be notified of all AEs that are serious, unexpected, and certainly, probably, or possibly related to the investigational product or serious reportable adverse events which could be associated with the trial procedures. This notification will be in the form of an Expedited Safety Report (ESR).

Upon receiving such notices, the Investigator must review and retain the ESR with the Investigator Brochure. Where required by local regulations or when there is a central Institutional Review Board (IRB)/Independent Ethics Committee (IEC) for the study, the Sponsor will submit the ESR to the appropriate IRB/IEC. The Investigator and IRB/IEC will determine if the informed consent requires revision. The Investigator should also comply with the IRB/IEC procedures for reporting any other safety information. Where

required, submission of ESRs by the Investigator to Health Authorities should be handled according to local regulations.

Periodically, according to the Investigator Brochure SOP, the Investigator Brochure will be updated and include new and relevant safety information. Until such time that an AE becomes identified in the Investigator Brochure, it should be considered unexpected, regardless of whether the AE has been the subject of a previous ESR.

